#### **Inclusion criteria:**

1. Patients will be referred from an orthopedic surgeon with confirmed diagnosis of lumbar spondylosis with imaging findings (MRI, CT or X-ray reports within the last 6 months) (Battié et al., 2014).
2. 2.Duration of patient's symptoms will be more than 3 months (Oliveira et al., 2022).
3. 3.Patients' age will range from 40-60 years (Kalichman & Hunter, 2008).
4. 4.Localized back pain and pain radiating to lower extremities with no distal involvement below knee with an NPRS more than 3 (Thompson et al., 2021).

[figure not shown]
#### **Exclusion Criteria:**

1. 1.Spinal or hip surgery history (Williams et al., 2022).
2. 2.Red Flags: Cauda equina syndrome, fracture, infection, malignancy (Finucane et al., 2020).
3. 3.Neurological Disorders: Parkinsonism, multiple sclerosis, or other neurological deficits (Odzimek et al., 2023).
4. 4.Inflammatory Conditions: Rheumatoid arthritis, ankylosing spondylitis, or infectious spinal disorders (Lee et al., 2018).
5. 5.Cognitive Impairment: Unable to understand or follow instructions (Martinez et al., 2024).
6. 6.Pregnancy.

### Sample Size Calculation:

A priori power analysis for ANOVA, repeated measures, within-between interactions was used with an effect size of 0.28, alpha level ( $\alpha$ ) = 0.05, and power ( $1-\beta$ ) = 0.95. The estimated sample size required was 54 participants, which was increased to account for potential dropouts as shown in **(Figure 1)**. Thus, the total sample will include 60 participants, randomly allocated into 3 equal groups (n= 20 per group).

Sample size was calculated using G\*Power software version 3.1.9.7, referencing effect size data of pain severity from a recent study studying the effects of thoracic and hip joint mobility exercise with lumbar stabilization exercise on pain and balance **(Choi and Kim, 2023)**.

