### **Combined thoracic and hip mobility exercises and low back pain**

**Choi and Kim. (2023)** examined the effects of **combining thoracic and hip joint mobility exercises** with lumbar stability training on pain and balance in 20 adult women with chronic low back pain. Participants were divided into two groups: the experimental group received thoracic and hip mobility plus lumbar stability exercises, while the control group received lumbar stability and general exercises. The intervention lasted six weeks, with sessions held three times per week. Pain was assessed using the Visual Analog Scale (VAS), and balance was measured with Basic Therapy 4. Both groups experienced significant pain reduction; however, only the experimental group showed improvements in both static and dynamic balance, though intergroup differences were not statistically significant. Study limitations include a small, gender-specific sample and short intervention duration.

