**Figure (9): Hip Mobility Exercises. (Demirtas et al., 2023)**

### **Data analysis and statistical design**

Statistical analysis will be performed using SPSS software for Windows, version 25.0 (SPSS, Inc., Chicago, IL) with Alpha level set at 0.05.

- Data will be screened for normality assumption, homogeneity of variance, and presence of extreme scores.
- Descriptive statistics will be calculated for all groups at baseline and after 6 weeks.
- ANOVA, repeated measures, within-between interactions model will be utilized to determine any differences between the mean change scores of groups regarding all outcomes.
- Bonferroni adjusted p-values for every outcome measure to protect against the possibility of type I error.

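### N=54 is correct for its inputs, but the cited 20-patient study, as the protocol describes it, does not support f=0.28 or the stated 0.95 power

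*Protocol*

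**What the plan says.** Under Sample Size Calculation (Chapter III), the protocol reports: "A priori power analysis for ANOVA, repeated measures, within-between interactions was used with an effect size of 0.28", with alpha 0.05 and power 0.95. It continues: "The estimated sample size required was 54 participants, which was increased to account for potential dropouts", so that "the total sample will include 60 participants, randomly allocated into 3 equal groups". The effect size is attributed to one source, "referencing effect size data of pain severity from a recent study studying the effects of thoracic and hip joint mobility exercise".

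Chapter II, in the section on combined thoracic and hip mobility exercises, describes that source. It had 20 women in two groups. One received thoracic and hip mobility plus lumbar stability exercises, the other lumbar stability plus general exercises. Pain fell significantly in both groups and balance improved only in the experimental group, "though intergroup differences were not statistically significant". No mean, SD, correlation, F or p-value is given.

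The text does not state the correlation between repeated measures, the effect-size option used in the software, or how 0.28 was obtained. Figure 1 is captioned as the sample size calculation, but its image is not in the copy read here.

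**The concern.** The 0.95 power is only as good as the 0.28 behind it. If 0.28 is the source's group-by-time effect on pain, it should agree with what the protocol says the source found, and it should measure a contrast like the one tested here. Both are doubtful.

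The stake is how a null result is read. All eleven hypotheses are worded as no difference between the three programmes. A non-significant result carrying a claimed 0.95 power invites the conclusion that thoracic and hip mobility add nothing, or are equivalent, when the real power may be clearly lower.

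**Working it through.** **Inputs.** From the protocol: f=0.28 (f²=0.0784), alpha 0.05, k=3 groups, m=2 measurements (baseline and 6 weeks), N=54 and 60; source N=20 in two groups. Assumed: pre-post correlation r (not in the text) and a 10/10 split in the source.

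**1. The plan's own figure.** On the software's default scale, λ = f²·N·m/(1−r), with df (k−1)(m−1) and (N−k)(m−1).
- N=54, r=0.5: λ = 0.0784×54×2/0.5 = 16.93, df (2, 51), power 0.956.
- N=51, r=0.5: λ = 15.99, power 0.944.

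So 54 is the smallest equal-group N reaching 0.95, and 54/0.90 = 60. With this design r=0.4 would give 63 and r=0.6 would give 45, so r=0.5 is a strong inference, though still an inference.

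**2. The same f and r in the source.** With k=2, m=2, N=20 and df (1, 18), the critical F is 4.41.
- F = 0.0784×20×2/0.5 = 6.27, p=0.022.
- With the factor 18/20 (error variance based on degrees of freedom rather than N): F = 5.64, p=0.029.

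An interaction of this size would have been significant. A higher correlation makes the tension worse: at r=0.7, p is 0.005 to 0.007.

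**3. Ways to reconcile this with a non-significant pain comparison.**
- *Lower correlation.* Setting F to the critical value 4.414 gives r = 1 − 0.0784×40/4.414 = 0.29, or 1 − 0.0784×36/4.414 = 0.36 with the 18/20 factor. If such an r carries over to this trial, power at N=54 is at most 0.86 to 0.90, and 75 to 69 patients are needed for 0.95. At r=0, power is 0.72 and the need is 102.
- *Smaller f, with r=0.5.* The largest non-significant f is √(4.414×0.5/40) = 0.235, or √(4.414×0.5/36) = 0.248. Power at N=54 is again 0.86 to 0.90, with 75 to 69 patients needed.
- *A different scale.* If 0.28 comes from a partial eta-squared (0.0784/1.0784 = 0.073), the source gives F = 0.0784×18 = 1.41, p=0.25, which fits non-significance. For this trial λ = 0.0784×51 = 4.00 and power is 0.39 at N=54. At N=60, λ = 0.0784×57 = 4.47 and power is 0.44. About 204 patients would be needed for 0.95.

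**4. The contrasts side by side (no correlation needed).**

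| | Cited study | This trial |
|---|---|---|
| Groups | 2 | 3 |
| Experimental | thoracic **and** hip mobility + stabilisation | thoracic **or** hip mobility + stabilisation |
| Comparator | stabilisation + general exercise | stabilisation alone, and the other component |

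The source effect is neither that of a single component nor the thoracic-versus-hip difference that the Statement of the Problem asks about.

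**5. What 60 patients can detect.** For a pairwise difference in change, d ≈ (z₁₋α/₂ + z_power)·√(2/n). At n=20 and alpha 0.05, 80% power: (1.960+0.842)×0.316 = 0.89. At 95%: (1.960+1.645)×0.316 = 1.14. The noncentral t raises these to about 0.90 and 1.16 SD. With alpha 0.05/3, it gives about 1.05 and 1.31 SD at n=20, and about 1.11 and 1.39 SD at n=18.

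**The case against.** The sample size arithmetic is right for its inputs; only the origin of f is open. That stands in full.

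A reader might go further and infer that 0.28 cannot be the source's pain interaction, because the protocol says that interaction was not significant. The documents do not support that. The clause in Chapter II names no outcome and directly follows the balance results, so it may not cover pain, and it does not mention a group-by-time test. The value r=0.5 is inferred from the answer 54, and the 10/10 split is assumed. The correlation among 20 women in the source need not equal the planning value for this trial. At a source correlation of 0.2, for example, f=0.28 gives p=0.063 to 0.077.

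A reader might also infer that true power is about 0.39. Nothing in the documents shows that a partial-eta-squared value was entered under the wrong option, so this remains one possibility.

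Settings such as r may appear in Figure 1, so their absence from the text is not a fault in itself. Borrowing from an imperfectly matched study is also common practice.

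Two things survive. If the clause does not cover pain, the protocol gives no between-group pain result from which 0.28 could come; the only pain result described is within-group, which is the wrong effect for an interaction test. And the mismatch of contrasts is plain on the page, whatever the correlation.

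**Conclusion.** The point holds in a limited form. N=54 is computed correctly, but the 0.95 power attached to it is not supported by the source named for it.

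The conflict with the source's reported non-significance depends on three assumptions: the clause covers pain, r was near 0.5, and the split was equal. If the clause does cover pain, each of the three reconciliations examined brings power at N=54 below 0.95: to at most about 0.86 to 0.90 through a lower correlation carried over to this trial or a smaller f, or to about 0.39 (0.44 at N=60) if the scale was wrong. The last figure is conditional and should not be reported as an established error.

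The second ground needs none of these assumptions: an effect of the combined package against a different comparator is not the effect of one component, nor the difference between the two. This should be corrected in the protocol, but it does not invalidate the trial.

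**What to change.** - Re-derive f from the source's group-by-time effect on pain. Choose the software's effect-size option that matches how f was obtained, and give the correlation used in the text.
- Reconcile the result with Chapter II by saying which outcomes the non-significant intergroup differences refer to.
- Replace 0.95 with the power that results, and acknowledge that the source tested the two components together.

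If the source cannot supply this, drop the source-based 0.95 claim, keep N=60 on feasibility grounds, and state the detectable pairwise difference in change:
- unadjusted, 20 per arm: about 0.9 SD (80% power) or 1.2 SD (95%);
- if the planned Bonferroni adjustment covers three pairwise contrasts (an assumption, since the analysis section does not say), 18 to 20 per arm: about 1.05 to 1.1 SD (80%) or 1.3 to 1.4 SD (95%).

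The adjusted figures are the safer ones to print, because the unadjusted ones ignore both the Bonferroni step and the planned dropout. The cost is a recalculation, some rewording and a less favourable stated power. Enrolment does not change.

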**Figure (1): Sample size calculation.**

### Ethical Consideration:

- The study's protocol will be reviewed and approved by the research ethical committee, faculty of physical therapy, Cairo University.
- All patients will sign an informed consent form after receiving information on the purpose of the study, procedures, possible benefits and risks, privacy and use of data **(Appendix I)**.

## Instrumentations:

### 1. Arabic version of numerical pain rating scale (NPRS-Ar):

The Numerical Pain Rating Scale is an 11-point (0-10) pain intensity measuring scale, it is a highly sensitive pain measuring scale and is widely preferred over Visual Analog Scale (VAS) due to its simplicity and clinical applicability (Alghadir et al., 2018). It ranges from zero to ten where the score zero represents no pain while the score 10 represents the worst possible pain (Kahl and Cleland, 2005; Ishtiaq et al., 2023). NPRS has high test-retest reliability ( $r = 0.95$  to  $0.96$ ) (Ferraz et al., 1990). Additionally, the NPRS demonstrates strong correlation with other established pain measurement scales, making it a reliable tool for clinical assessments (Alghadir et al., 2018). It has been translated and validated into Arabic language by Alghadir et al., (2016) (Appendix II).

[figure not shown]

Figure (2): Arabic NPRS

### 2. Modified Oswestry Disability Index Arabic Version (MODI-Ar):

The Modified Oswestry Disability Index is a 10-item disease-specific questionnaire measuring functional disability caused by low back pain in the following categories: pain intensity, personal care, lifting, walking, sitting, standing, sleeping, social life, traveling, and employment/homemaking (Fairbank & Pynsent, 2000).

The modified version was used as it replaced the "sex life" category with "employment/homemaking" that is more culturally appropriate and clinically relevant to multinational populations and particularly in Arabic-speaking populations where the issue of sexual relationships may be culturally sensitive (Ramzy, 2008).

[figure not shown]
MODI-Ar has excellent internal consistency (Cronbach's  $\alpha = 0.94$ ) and test-retest reliability (ICC = 0.91). Construct validity demonstrates good correlation with SF-36 physical functioning ( $r = -0.82$ ) and moderate correlation with pain intensity ( $r = 0.67$ ) (Alnahdi, 2025).

It was translated and validated into Arabic language by Alnahdi, (2025) (Appendix III).

### 3. Back Range of Motion Device (BROM):

The BROM device is a gravity-dependent dual inclinometer system that is used specifically to measure spinal range of motion in the sagittal and frontal planes with pelvic compensation movements excluded as shown in (figure 3) (Chen et al., 2022). BROM has high inter-rater reliability (ICC = 0.92-0.96) and intra-rater reliability (ICC = 0.94-0.98) for the measurement of lumbar flexion and extension. Concurrent validity with radiographic measurements is highly correlated ( $r = 0.87$ - $0.93$ ) (Kumar & Singh, 2021). It has the following

advantages; High accuracy, being portable and simple to use in the clinical setting. Model used in this study: BROM II Deluxe (Performance Attainment Associates, Roseville, MN, USA).

**Figure (3): Back Range of Motion Device (BROM). (Seo et al., 2022)**

#### **4. Spinal Mobility Test (Modified Schober Test):**

The Modified Schober Test is a clinical measurement of lumbar spine flexion where 15cm above and 5cm below the lumbosacral junction (L5-S1) is marked and the difference in distance is measured on forward flexion (**Kumar et al., 2019**). Inter-rater reliability (ICC = 0.89-0.94) and intra-rater reliability (ICC = 0.92-0.96). Criterion validity with radiographic lumbar flexion measurements with strong correlation ( $r = 0.81-0.86$ ) (**Tousignant et al., 2005**). Normal Values: 5-7cm increase in distance is normal during full flexion in healthy adults (**Hershkovich et al., 2022**).

#### **5. Short Form 36 Health Survey Arabic version (SF-36-Ar):**

The SF-36 is a general health-related quality of life instrument measuring 8 domains: physical functioning, role limitations caused by physical problems, pain, general health perceptions, vitality, social functioning, role limitations caused by emotional problems, and mental health (**Ware & Sherbourne, 1992**). Each domain is scored 0-100, and higher scores indicate better health status. Physical Component Summary (PCS) and Mental Component Summary (MCS) provide overall physical and mental health scores (**Johnson et al., 2012**).

The Arabic version was validated by **El-Kalla, (2016)** to fit Arab populations, including simplifying language and providing culturally relevant examples (**Appendix IV**). SF-36 Arabic version demonstrated high internal consistency across all domains (Cronbach's  $\alpha = 0.83-0.94$ ) and test-retest reliability (ICC = 0.78-0.92). Construct validity confirmed through confirmatory factor analysis for the 8-factor structure (**El-Kalla, 2016**).

#### **6. Tampa Scale for Kinesiophobia Arabic Version (Tampa-Ar):**

The Tampa Scale for Kinesiophobia is a 17-item questionnaire that measures fear of movement and re-injury in patients with chronic

musculoskeletal pain, on a 4-point Likert scale (1=strongly disagree to 4=strongly agree) (Weermeijer & Meulders, 2018). It varies from 17-68, where higher scores indicate a greater fear of movement. Cut-off point of  $\geq 37$  indicates high kinesiophobia in the Arabic-speaking population (Al-Shudifat et al., 2020).

Adaptation into Arabic was done by Al-Shudifat et al., (2020) following guidelines with forward-backward translation, discussion with an expert panel, and pilot testing on chronic low back pain patients (Appendix V). Tampa-Ar shows good internal consistency (Cronbach's  $\alpha = 0.86$ ) and test-retest reliability (ICC = 0.84-0.89) (Al-Shudifat et al., 2020).

### **Assessment Procedures**

All assessments will be conducted at baseline (pre-treatment) and **after 6 weeks** of intervention (post-treatment) by **blinded assessors** to ensure objectivity and minimize bias. Assessment procedures will include:

#### **1. Pain severity:**

Using the Arabic NPRS (Appendix II), Patients will select a value between (0-10) based on intensity of pain. Where (0) means no pain and (10) means maximum pain experienced (Kahl and Cleland, 2005; Ishtiaq et al., 2023).

#### **2. Disability:**

Using the Arabic MODI (Appendix III), Patients will be instructed to choose the best answer of the possible answers which describes the level of function and disability during daily activities in each of items of the questionnaire (Alnahdi, 2025).

#### **3. Lumbar Range of motion:**

The Back Range of Motion (BROM) device will be utilized to measure the lumbar range of motion (ROM), as a valid and reliable measure of spinal motion (Kumar & Singh, 2021; Chen et al., 2022), according to established procedures (Madson et al., 1999). After palpating and marking the spinous processes of T-12 and S1 with adhesive dots, a warm-up trial for each plane of motion will be completed by patients. The BROM device will be used to measure active ROM in the order of flexion/extension, right/left lateral flexion, and right/left rotation. Once the data for each movement was taken, the BROM device was removed, and the skin markers were reapplied after a 10-15 second rest period. Each motion will have three trials, and data from the three trials will be averaged and used for analysis in order to maximize reliability.

##### **a- For flexion/extension measurements:**

Each patient will stand upright and assume a comfortable erect posture with body weight evenly distributed and feet shoulder-width apart. The BROM unit will be mounted by the examiner. The patient will be asked to grasp the ends of

each Velcro strap and cross them near the symphysis pubis, where they will become firmly attached to each other. The removable L-shaped slide arm for the flexion and extension unit will be placed in the slot of the frame, and the short arm tip will be placed on the adhesive dot marking the T-12 spinous process.

The therapist will record the starting position on the upper scale of the frame mounted to the sacrum. The examiner will hold the tip of the short side of the slide arm unit in constant contact with the patient's T-12 spinous process and will instruct to: "Bend forward as far as you can, trying to reach your fingertips to the floor. Do not bend farther than is comfortable, and do not cause any back pain". The examiner will stand on the opposite side of patient. The initial flexion reading will be subtracted from the full flexion reading to obtain full trunk flexion. Then the examiner will tell the patient to return to the starting position, as shown in **(figure 4)** (Madson et al., 1999).

After that, the examiner will instruct the patient to, "Bend backward as far as you can, and keeping your hands alongside the back of your thighs. Do not bend farther than is comfortable, and do not cause back pain". The examiner will keep constant contact of the L-shaped arm against the red dot marking the T-12 spinous process. The difference between the baseline measurement and the position of full extension will be recorded as trunk extension. Then the examiner will ask the patient to return to the starting position, as shown in **(figure 4)** (Madson et al., 1999).

**Figure (4): Flexion/extension measurements. (Madson et al., 1999)**

#### **b- For lateral flexion measurements:**

Patients will stand parallel to a wall to avoid the substitution pattern of forward trunk flexion. The examiner will place the BROM unit parallel to and along a line over the red dot marking the T-12 spinous process. The lower ribs of the patient will be grasped by the examiner's fingers to keep the BROM unit in place. The needle of the inclinometer pointed to zero, marking the starting position for lateral flexion. When the patient flexes laterally, the BROM unit becomes a part of the patient's truncal movement. Instructions will be given to the patient: "Slide your right hand down the side of your right thigh and try to

reach for your knee. Be sure to keep your weight on your left leg and foot to avoid hiking your left hip and lifting your left heel off the floor. Do not bend farther than is comfortable, and do not cause back pain". The examiner will stand behind the patient during measurement. The same commands will be given for left lateral flexion measurements except that the patient will place body weight on the right leg and foot, as shown in **(figure 5) (Madson et al., 1999)**.

**Figure (5): Lateral flexion measurements. (Madson et al., 1999)**

**c- For rotation measurements:**

During rotation measurements, the magnetic yoke will be placed around the patient's pelvis at the level of the iliac crests. A buckle held the magnetic yoke in place. The patient will sit on a stool facing west so that the end of the magnet with north polarity will be aligned in the correct direction. The examiner will place the BROM unit parallel to the ground and along a line over the red dot marking the T-12 spinous process. The lower ribs of the patient will be grasped by the examiner's fingers to keep the BROM unit in place. During axial rotation of the spine, the BROM unit becomes a part of the patient's truncal movement, as shown in **(figure 6) (Madson et al., 1999)**.

Each patient will be told to place hands across chest and then instructed, "Twist your trunk to the right as far as you can go. Do not twist farther than is comfortable, and do not cause back pain". The examiner will stand behind the patient. The same commands will be given for left rotation, as shown in **(figure 6) (Madson et al., 1999)**.

**Figure (6): Rotation measurements. (Madson et al., 1999)**

#### **4. Spinal mobility:**

Using the Modified Schober Test, Patient will be standing. The examiner will mark both posterior superior iliac spine (PSIS) and then will draw a horizontal line at the center of both marks. A second line is marked 5 cm below the first line. A third line is marked 10 cm above the first line. Patient will be instructed to flex forward as if attempting to touch his/her toes. The examiner re-measures the distance between the top and bottom line (**Rezvani et al., 2012**). Three trials will be conducted and the mean of the three trials will be chosen for the purpose of data analysis

